10.4 Primary efficacy endpoint analysis

Procedural success rate will be estimated and reported with 95% confidence interval.

10.5 Secondary endpoint analysis

All event rates within 48 hours of procedure will be estimated and reported with 95% confidence interval.

10.6 Safety evaluation

Kaplan-Meier curve will be used to construct 1-year cumulative event rates with 95% confidence interval.

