4.2.2 Follow-up at 12 months: telephone contact

The following information will be captured during this 12-month follow-up visit: Symptoms (CCS score), medications (antiplatelet therapy, statins, non-statins LDL lowering therapy), outcomes (death, MI, TLR, stent thrombosis, and stroke).

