8.2 Safety index

The following safety data will be collected over the 12-months follow-up period:

1. All-cause death (cardiac/non-cardiac/sudden death/unknown)
2. Myocardial infarction
 - a. Subset analysis on target vessel MI (TVMI) in those with data on repeat coronary angiography
3. Target lesion revascularization (TLR)
4. Definite/probable stent thrombosis
5. Major cardiovascular events (MACE)
 - a. Defined as composite endpoint of cardiac death, MI, TLR, and stent thrombosis
6. Stroke
7. Device related adverse events
 - a. Includes but are not limited to rotawire fracture/ breakage, rotawire unravelling/ fraying, burr dislodgement/ fracture and burr entrapment

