10.1.2 Assumptions

The target sample size is calculated based on the following assumptions:

1. The proportion of RA-related complications is 5%
2. 95% confidence intervals width is 3%.
3. Up to 20% of patients are assumed to drop out of this study

Sample							
Confidence	Size	Target	Actual	Proportion	Lower	Upper	Width if
Level	(N)	Width	Width	(P)	Limit	Limit	P = 0.5
0.95	1118	0.02	0.02	0.03	0.02	0.04	0.059
0.95	1476	0.02	0.02	0.04	0.03	0.05	0.051
0.95	1825	0.02	0.02	0.05	0.04	0.06	0.046
0.95	2167	0.02	0.02	0.06	0.05	0.07	0.042
0.95	497	0.03	0.03	0.03	0.015	0.045	0.088
0.95	656	0.03	0.03	0.04	0.025	0.055	0.077
0.95	811	0.03	0.03	0.05	0.035	0.065	0.069
0.95	963	0.03	0.03	0.06	0.045	0.075	0.063
0.95	280	0.04	0.04	0.03	0.01	0.05	0.117
0.95	369	0.04	0.04	0.04	0.02	0.06	0.102
0.95	457	0.04	0.04	0.05	0.03	0.07	0.092
0.95	542	0.04	0.04	0.06	0.04	0.08	0.084

Table 1: Numeric Results for Two-Sided Confidence Intervals for One Proportion Confidence Interval

Formula: Simple Asymptotic

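### Kaplan-Meier for every 1-year event rate slightly overstates MI, TLR, stent thrombosis, stroke and MACE, because deaths that preclude these events would be censored

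*Protocol*

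**What the plan says.** Section 10.6 of the protocol consists of one sentence: "Kaplan-Meier curve will be used to construct 1-year cumulative event rates with 95% confidence interval". It does not list the events it covers and does not say what happens to a patient who dies before having the event.

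The events are in Section 8.2 (Safety index), introduced by "The following safety data will be collected over the 12-months follow-up period". They are all-cause death, MI, TLR, definite or probable stent thrombosis, MACE, stroke and device-related events. MACE is "Defined as composite endpoint of cardiac death, MI, TLR, and stent thrombosis", so a death from a non-cardiac cause is not a MACE event. Section 4.2.2 collects the same kind of outcomes at the 12-month call: "outcomes (death, MI, TLR, stent thrombosis, and stroke".

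Nowhere does the protocol mention competing risks or a cumulative incidence function.

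**The concern.** Kaplan-Meier assumes that a censored patient could still have the event later, at the same rate as those who remain under observation. That is reasonable for a patient lost to follow-up and impossible for one who has died. With deaths censored, one minus Kaplan-Meier describes a hypothetical population in which nobody dies first, and it cannot fall below the proportion of real patients who have the event within the year.

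For MI, TLR, stent thrombosis and stroke, the competing event is any death that comes first. For MACE it is death not classed as cardiac. All-cause death has no competing event, so Kaplan-Meier is right for it.

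The registry has a single arm, and these 1-year rates are reported as absolute figures, so no comparison between arms would cancel the bias. Unlike sampling error, it does not shrink as N grows.

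**Working it through.** **Precision the plan works with.** Section 10.1.2 assumes a 5% complication proportion and a 95% interval of full width 3 points, by the simple asymptotic formula:

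n = 4 z² p(1 − p) / w² = 4 × 1.95996² × 0.05 × 0.95 / 0.03² = 810.97, rounded up to 811.

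This agrees with the protocol's table. Allowing for 20% dropout, 811 / 0.80 = 1014, close to the stated 1000. That calculation concerns RA-related complications, not the 1-year events, but it gives a yardstick. At N = 1000 and a 5% rate, the 95% half-width is 1.96 × √(0.05 × 0.95 / 1000) = 1.35 points. At 10% it is 1.86 points.

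**Size of the bias.** The protocol states neither a 1-year event rate nor a 1-year mortality, so both are assumptions here. Appendix 1 lists deaths of 0.0% to 4.0% in earlier series, with no time horizon.

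Let E be the true 1-year incidence of the event and D the 1-year incidence of competing death, that is, death before the event. With constant hazards:

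- total hazard L = −ln(1 − E − D)
- event hazard h = L × E / (E + D)
- reported value = 1 − exp(−h)

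For E = 5%:

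| D | L | h | Reported | Excess (points) |
|---|---|---|---|---|
| 1% | 0.0619 | 0.0516 | 5.03% | 0.03 |
| 4% | 0.0943 | 0.0524 | 5.10% | 0.10 |
| 5% | 0.1054 | 0.0527 | 5.13% | 0.13 |
| 10% | 0.1625 | 0.0542 | 5.27% | 0.27 |

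A simulation of one million patients at E = 5%, D = 10% gave 5.29% by Kaplan-Meier against 5.01% actual incidence, in line with the last row.

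At other event rates: E = 2% is reported as 2.05% at D = 5% and 2.11% at D = 10%; E = 10% is reported as 10.27% and 10.56%.

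**Timing of deaths.** The bias is largest if all competing deaths come at the very start. The reported value is then E / (1 − D): for E = 5%, 5.26% at D = 5% and 5.56% at D = 10%. If the deaths come after all the events, there is no bias.

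**MACE.** Only deaths not classed as cardiac compete. If, for illustration, half of a 4% mortality were non-cardiac, D would be 2%, and a true 5% would be reported as 5.05% rather than 5.10%. At a given incidence and mortality the bias is therefore smaller for MACE.

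**The case against.** The strongest objection is size. In the constant-hazard table the excess is at most 0.27 points against a half-width of 1.35. No test or decision rule uses the 1-year rates, so it is hard to see a conclusion changing. This stands, and it is why the point is minor.

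Second, Section 10.6 is brief, and an analysis plan that is not at hand might say how death is handled. Censoring at death is the usual reading, not a stated rule. This stands in part. However, the protocol already names the estimator for all these rates without qualification, so an analysis plan that used another would depart from it.

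A reader might infer more than the documents support:

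- **That the registry's main results are biased.** They are not. Procedural success, the RA-related complication rate and the 48-hour event rates are procedural or short-term and are not assigned to Kaplan-Meier. All-cause death, including the secondary endpoint of death at 1 year, is correctly estimated by it.
- **That the overstatement is large because mortality will be 10% to 15%.** Nothing in the protocol supports those rates. Total mortality also overstates what competes, since a death that follows the event does not compete with it.
- **That the bias distorts the chronic kidney disease or low-LVEF subgroups.** It would be larger wherever mortality is higher. But Section 10.7 says only that subgroups may be used, Section 10.6 does not call for curves by subgroup, and no subgroup mortality is given.

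**Conclusion.** The point holds as a minor one. Followed in the ordinary way, Section 10.6 overstates the 1-year cumulative incidence of MI, TLR, stent thrombosis, stroke and MACE. The direction is certain whenever competing deaths precede later events. The size rests on assumed rates and constant hazards: about 0.03 to 0.27 points on a true 5% for competing death between 1% and 10%, and about 0.10 points at 4%, the highest death rate shown in Appendix 1. All of these are well inside the sampling uncertainty at N = 1000. The case for changing it is that the better estimator is readily available and uses data already being collected.

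**What to change.** In Section 10.6, keep Kaplan-Meier for all-cause death. For MI, TLR, stent thrombosis and stroke, specify the Aalen-Johansen cumulative incidence with 95% confidence intervals and death as the competing event. For MACE, specify the same estimator with non-cardiac death as the competing event. Patients lost to follow-up remain censored; crude proportions would not handle them.

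One rule must be added for MACE. Section 8.2 records death as "All-cause death (cardiac/non-cardiac/sudden death/unknown", and the last two classes are neither plainly cardiac nor plainly competing. The protocol should state whether each counts as cardiac death, and so as a MACE event, or as a competing event. This can outweigh the choice of estimator: for every 10 such deaths per 1000 patients without an earlier MACE event, the MACE rate moves by up to 1 point.

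The cost is a few lines of text, slightly more analysis work and one classification rule. No new data are needed, because cause of death is already collected.

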10.7 Sub-group analysis

This study will collect all subjects who have undergone calcium debulking therapy and evaluate real-world clinical outcomes

The following sub-groups (but not limited to) may be utilised for analysis:

- (i) Acute coronary syndrome
- (ii) Lesion length
- (iii) Bifurcation lesions
- (iv) Multiple overlapping stents (≥ 2 stents for each epicardial coronary artery)
- (v) Chronic kidney disease

- (vi) Multivessel disease (\geq 2 vessel CAD)
- (vii) Left main (LM) equivalent
- (viii) Chronic total occlusions (CTO)
- (ix) Severely impaired LVEF i.e. \leq 30%
- (x) IVUS subgroup

11 Study Management

11.1 Statement

This study complies with the requirements of the current Declaration of Helsinki as well as other relevant national regulations

11.2 Ethical section

In accordance to national policies and regulations, the site study investigators must provide the Ethics Committee with relevant study documents as required.

A copy of the approval from the local Ethics Committee together with the list of review documents must be submitted to the primary site i.e. National Heart Centre Singapore (NHCS) before the device will be delivered to the study sites. The approval document from the Ethics Committee must also be accompanied by a list detailing all the members involved in the approval and their respective roles in the committee.

Approval from Ethics Committee is mandatory prior to initiation of clinical trial.

Any changes to the study protocol must be submitted to the Ethics Committee for approval. Throughout the study, any serious or unintended adverse events pertaining to safety of patients must be reported to the Ethics Committee.

11.3 Verification of original records

Study investigators must ensure that all data obtained during this study is properly secured and encrypted to protect the privacy of subjects involved. In addition, study investigators must also consent to audit/ verification of database by auditors/ inspectors to ensure accuracy and accountability of data collected as well as update on progress of study. In the unfortunate event that the original records cannot be verified, the study investigator will need to assist the auditor in quality control of the data.

11.4 Quality assurance and audit

The study will be audited by personnel authorized by National Heart Centre Singapore/ Boston Scientific Corporation. Quality auditors will have access to all medical records, research-related documents/ correspondences, and informed consent for this study.

11.5 Informed Consent

It is the responsibility of the study investigator to explain the purpose, methods, benefits, and potential risks of this clinical trial to each subject. An informed consent (both written and verbal) must be obtained from the subject prior to inclusion in this study. Informed consent must be dated and signed by the participant him or herself. Participants who decline to provide informed consent will be excluded from this study. A copy of the signed informed consent and information sheet will be given to the participants.

By signing the informed consent form, the participant has agreed to allow National Heart Centre Singapore and Boston Scientific Corporation auditors to verify the data.

11.6 Modification of study protocol

Once the final version of the study protocol has been agreed upon, any further modifications to the protocol will be subjected to a detailed review of proposed changes with the proposer to initial against the proposed changes with date and time.

All proposed changes must be approved in writing by the Ethics Committee. All documents will need to be submitted to National Heart Centre Singapore (NHCS)

11.7 Case report form (CRF)

Operators/ institution coordinators will fill up hardcopy and/or electronic (web-based) forms including patient's baseline demographics, co-morbidities, clinical data, laboratory test results, echocardiography results, coronary angiography findings with subsequent interventions performed as well as follow-up clinical and laboratory results. Note that while detailed data for individual patients will only be collected if there is informed consent, data from each institution will also be collected for aggregate data regarding procedural volume (eg. Of total cases with debulking therapy and specifically for rotablator). This will give a sense of representativeness of data collected.

11.8 Audit

NHCS will request for participating centers to provide updates on recruitment progress as well as clinical outcomes of existing patients at regular intervals.

Finally, all original data collection forms, records, laboratory results must be readily available at every time point to all study investigators and auditors.

11.9 Confidentiality agreement and patient privacy

Study investigators must ensure the confidentiality of the information provided or disclose the requisite information as required with the authorization from NHCS.

The researcher must not disclose any confidential information obtained from NHCS, Boston Scientific, or from this study to third parties.

Researcher must ensure that the data is anonymized. It is imperative that all documents submitted to NHCS or Boston Scientific is labelled with study index number and that participants personal details cannot be retrieved from the documents.

12. Publications

National Heart Centre Singapore (NHCS), as the primary site, will hold exclusive rights to this study. All study site investigators will be involved in the drafting of manuscripts related to this study. As this is a multicenter study, investigators are not allowed to write/ submit a manuscript until the final analysis from the multicenter study is completed, unless it is approved by NHCS. With regards to manuscripts and publications, NHCS reserves the right to determine the final outcome.

13. Data archiving

In accordance to regulations, study investigators should properly preserve the original records of the research. All clinical research data must be kept for at least 5 years from the start of data collection. It is the responsibility of the primary site to inform the study investigators when such information is no longer required to be saved.

14. References

1. Popma JJ BT. Qualitative and Quantitative Angiography. In: E. T, ed. *Textbook of Interventional Cardiology*. WB Saunders, Philaadelphia, PA; 1994:1052-1068.

15.1 Appendix 1: Contemporary data on RA-related complication rates

Table 3: Complications of Rotational Atherectomy in the Drug-eluting Stent Era

Study	n	Death (%)	MI (%)	Dissection (%)	Perforation (%)	Slow Flow/No Reflow (%)
PREPARE-CALC, 2018 ⁵³	100	0.0	2.0	3.0	4.0	2.0
Kawamoto et al, 2016 ⁴⁸	1176	0.6	7.4	7.0	1.0	1.1
Sakakura et al, 2016 ⁸³	13,335	0.6	–	–	–	–
Eftychiou et al, 2016 ⁸²	518	0.6	–	–	1.4	0.6
ROTAXUS, 2013 ¹¹	120	1.7	1.7	3.3	1.7	0.0
Abdel-Wahab et al, 2013 ⁴⁶	205	1.5	2.4	4.4	0.5	2.0
Naito et al, 2012 ⁷⁴	233	0.0	1.3	1.7	0.4	–
Benezet et al, 2011 ⁴⁷	102	1.0	1.0	2.9	0.0	–
Garcia de Lara et al, 2010 ⁷³	50	4.0	14.0	2.0	2.0	0.0
Rathore et al, 2010 ⁴⁸	391	1.0	6.9	5.9	2.0	2.6
Vaquerizo et al, 2010 ⁴⁹	63	0.0	3.2	–	–	–
Furuichi et al, 2009 ⁵⁰	95	0.0	3.2	2.1	1.1	1.1
Clavijo et al, 2006 ⁵¹	81	0.0	19.8	1.9	–	–

Source: Tomey et al. 2014.⁵ Adapted with permission from Elsevier © The American College of Cardiology Foundation.

15.2 Appendix 2: Definition and breakdown of RA-related complications

Paper	Study	Modality	Definition	Outcomes in RA
Safian et. al CARAT trial CCI 2001	Prospective, randomised, multicenter	RA (large vs small burr)	Any of (i) severe dissection (ii) no reflow (iii) side branch occlusion	Total 12.1%; severe dissection 6.3%, no reflow (2.3%), sidebranch occlusion (3.5%)
				Breakdown by burr size: large (12.7%) vs small (5.1%), p < 0.05
Abdel-Wahab et. al PREPARE CALC trial CCI 2018	Prospective, randomised, multicenter	RA vs modified balloon (MB)	Any of (i) large dissection (ii) perforations (iii) no/slow reflow (iv) side branch occlusion	Large dissection (3%), Perforation (4%), No/slow reflow (2%), side branch occlusion (6%)
Lee et. al AJC 2017	Retrospective, single center	RA vs OA	Any of (i) perforation (ii) dissection leading to less than TIMI 3 flow (iii) no reflow	Perforation/ dissection (0%), no- reflow (7%)
Chen et. al. J Interven Cardiol 2018	Retrospective, single center	RA of main vessel (MV) vs side branch +/- main vessel (SB-MV)	Any of (i) No flow (ii) SB perforation (iii) Wire transection	No flow in SB (4.2%) vs SB-MV (2.9%), perforation in SB (6.3%) vs SB-MV (0.8%), wire transection SB (0%) vs SB-MV (0.8%)

Breakdown by each complication:

- (i) Severe dissection: 1.7 – 5.9%
 - a. Lee et. al AJC 2017: any dissection that resulted in < TIMI 3 flow
 - b. Safian et. al CARAT trial 2001: any dissection that requires stenting
 - c. Abdel-Wahab et al. PREPARE-CALC 2018: large dissection > 5mm
 - d. Ali et. al DISRUPT CAD II 2019: any dissection Type D-F that impaired flow
 - e. NHLBI (based on depth and breadth of dissection + presence of intimal flap)

The National Heart, Lung and Blood Institute (NHLBI) classification system for intimal tears

Type A dissections represent minor radiolucent areas within the coronary lumen during contrast injection with little or no persistence of contrast after the dye has cleared

[figure not shown]
Type B dissections are parallel tracts or a double lumen separated by a radiolucent area during contrast injection, with minimal or no persistence after dye clearance

Type C dissections appear as contrast outside the coronary lumen ("extraluminal cap") with persistence of contrast after dye has cleared from the lumen

Type D dissections represent spiral ("barber shop pole") luminal filling defects, frequently with excessive contrast staining of the dissected false lumen

Type E dissections appear as new, persistent filling defects within the coronary lumen

Type F dissections represent those that lead to total occlusion of the coronary lumen without distal antegrade flow

- (ii) Slow flow/ no reflow: 2.5%
- (iii) Perforation: 2%
 - a. All papers did not define/ classify perforation type. They included all types of perforation in analysis for complications

